**Treatment Compliance for Fluticasone Propionate (FP) and Salmeterol (SAL)**

- Treatment compliance will be calculated based on the formula:  

$$\text{Treatment Compliance} = \frac{\text{Number of Actual Doses}}{(\text{Planned Treatment Duration in Days} * \text{Frequency})} * 100$$
- Frequency is 2 for BID and 1 for QD. Treatment compliance could be greater than 100% if there are events of overdose. Cumulative compliance (since Day 1) by each background therapy will be calculated.
- Planned Treatment Duration is defined according to the schedule of activities.
- Compliance will be summarized by the following categories:  
 <80%,  
 ≥ 80% to < 95%,  
 ≥95% to <105%,  
 ≥ 105% to <120% and  
 ≥120%

**Extent of Exposure (Therapeutic Coverage)**

- IP is administered approximately every 4 weeks and each dose viewed as providing therapeutic coverage for 4 weeks (28 days).
- Number of days of exposure to study drug will be calculated based on the formula:  

$$\text{Duration of Exposure in Days} = \text{Study Treatment Last Dose Date} - (\text{Study Treatment First Dose Date}) + 29$$
- The only exception to this will be when a participant dies in which case  

$$\text{Duration of Exposure in Days} = \text{Death Date} - (\text{Study Treatment First Dose Date}) + 1$$

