## 2.4. Study Design

Overview of Study Design and Key Features	
 
The diagram illustrates the study design timeline from Week 0 to Week 28. It is divided into a Treatment Phase (Weeks 0-12) and a Follow Up Phase (Weeks 16-28). In the Treatment Phase, participants receive a double-blind study treatment every 4 weeks, either GSK3772847 or Placebo, at Weeks 0, 4, 8, and 12. Simultaneously, background therapy is reduced from LABA, Sal, and ICS at Week 0 to FP 500 BID at Week 2, and then further reduced to FP 250 BID, FP 100 BID, and FP 50 BID by Week 10. In the Follow Up Phase, participants receive LABA and ICS from Week 16 to Week 28. Visits are labeled V0 through V14, with an ETP Visit at Week 11.
	
Design Features	
 
The study is a Phase IIa, multicenter, randomised, placebo-controlled, double-blind, stratified, parallel group study.
 

Dosing	
 
Participants will have a two-week Run-in period in which they take a background therapy of fluticasone propionate (FP)/salmeterol 500/50 mcg BID.
 
Following run-in they will be randomised to receive four doses of either GSK3772847 or Placebo intravenously (Week 0, 4, 8 and 12) whilst initially still receiving background FP/Salmeterol 500/50 mcg BID.
 
At Week 2 background therapy will be changed to FP 500 mcg BID only. This will then be reduced by approximately 50 % every two weeks until complete FP discontinuation at Week 10.
 

Treatment Assignment	
 
Participants will be randomised in a 1:1 ratio to receive four doses of either GSK3772847 or Placebo administered intravenously every 4 weeks.
 
Randomisation will be stratified based on participants' baseline peripheral blood eosinophil count which is measured at screening (<150 cells/<math>\mu</math>L, <math>\geq</math>150 cells/<math>\mu</math>L), Randomisation will also be stratified according to whether participants consent to the sputum sub study.
 

Overview of Study Design and Key Features	

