**7.2.4.1. Statistical Methodology Specification**

Endpoint / Variables

 
Time to loss of asthma control.
 

Strategy for Intercurrent (Post-Randomisation) Events

 
Both primary and secondary estimands (Section 7.1.4) will be examined. It is important to assess both estimands as data is missing after withdrawal or loss of asthma control. This could produce biased estimates, as loss of control and therefore missing data is related to study treatment, and so the secondary estimand where missing data is set as non-responders must also be considered.
 

Model Specification

 
Time to loss of asthma control will be analysed on the Modified Intent-to-Treat excluding GCP non-compliant subjects (Loss of Control) population using Kaplan-Meier analysis (Proc lifetest). Within the Kaplan Meier plot participants will either be counted as an event or they will be censored.
 
A log rank test will be performed to test for difference between the time to loss of asthma control on Placebo compared with GSK3772847
 
 
Primary Estimand:
 
 
Events: Participants who experience loss of asthma control during the study
 
Censoring: Participants who discontinue investigational product for reasons other than loss of asthma control will be censored at the date of early withdrawal from study treatment. Participants who successfully complete the 16 week treatment period will be censored at 113 days (16 weeks + 1 day).
 
 
Secondary Estimand:
 
 
Events: Participants who experience loss of asthma control during the study or who discontinue investigational product for reasons other than loss of asthma control (date of event will be set to date of early withdrawal from study treatment).
 
Censoring: Participants who successfully complete the 16 week treatment period will be censored at 113 days (16 weeks + 1 day).
 

Time to event/censoring = Date of event/censoring – Treatment start date + 1. If participants experience multiple reasons for loss of control then the earliest date will be used as described in Section 0.

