

Rate of Events per 1000 Treatment Years
 
Rate of events per 1000 treatment years will be calculated using:
 
Rate = number of events * 1000 / total treatment exposure in years where subjects can contribute more than one event.
 
This is equivalent to: Rate = number of events * 1000 / (number of subjects in treatment group * mean treatment exposure in years).

--

Maximum/Minimum Definitions for Vital Signs Data
 
Maximum and Minimum: Maximum and Minimum post-randomisation value over all time-points (including scheduled and unscheduled assessments) will be presented.

---

FEV1

Absolute Reversibility
 
Absolute reversibility (mL) = (post-bronchodilator FEV1 – pre-bronchodilator FEV1)

Percent Reversibility
 
Definition of Percentage Reversibility as a percentage of predicted FEV1 = ((post-bronchodilator FEV1– pre-bronchodilator FEV1) / predicted FEV1) x 100%
 
Definition of Percentage Reversibility as a percentage of pre-bronchodilator FEV1 = ((post-bronchodilator FEV1– pre-bronchodilator FEV1) / pre-bronchodilator FEV1) x 100%

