## 12.10.5. Efficacy Tables

Efficacy: Tables					
No.	Population	IDSL / Example Shell	Title	Programming Notes	Deliverable [Priority]
Exposure					
2.1.	SAFF_ALL	EX1	Summary of Exposure to Study Treatment	ICH E3	ETP, SAC
Primary Endpoint: Loss of Asthma Control Weeks 0-16					
2.2.	mITT_LoC	EFF_T01	Summary of Loss of Asthma Control	Include overall loss of control, each component and the combination of exacerbation or inability to titrate.	ETP, SAC
2.3.	mITT_LoC	EFF_T02	Summary of On-treatment Intercurrent Events		ETP, SAC
2.4.	mITT_LoC	EFF_T03	Bayesian Analysis of Loss of Asthma Control Over Weeks 0-16 (Primary Estimand)		ETP, SAC
2.5.	mITT_LoC	EFF_T04	Frequentist Analysis of Loss of Asthma Control Over Weeks 0-16 (Primary Estimand)		ETP, SAC
2.6.	mITT_LoC	EFF_T03	Bayesian Analysis of Loss of Asthma Control Over Weeks 0-16 (Secondary Estimand)		ETP, SAC
2.7.	mITT_LoC	EFF_T04	Frequentist Analysis of Loss of Asthma Control Over Weeks 0-16 (Secondary Estimand)		ETP, SAC
Secondary Endpoint: Loss of Asthma Control Weeks 0-6					
2.8.	mITT_LoC	EFF_T03	Bayesian Analysis of Loss of Asthma Control Over Weeks 0-6 (Primary Estimand)		ETP, SAC
2.9.	mITT_LoC	EFF_T04	Frequentist Analysis of Loss of Asthma Control Over Weeks 0-6 (Primary Estimand)		ETP, SAC
2.10.	mITT_LoC	EFF_T03	Bayesian Analysis of Loss of Asthma Control Over Weeks 0-6 (Secondary Estimand)		ETP, SAC

Efficacy: Tables					
No.	Population	IDSL / Example Shell	Title	Programming Notes	Deliverable [Priority]
2.11.	mITT_LoC	EFF_T04	Frequentist Analysis of Loss of Asthma Control Over Weeks 0-6 (Secondary Estimand)		ETP, SAC
Secondary Endpoints: Time to Loss of Asthma Control					
2.12.	mITT_LoC	EFF_T05	Summary and Analysis of Time to Loss of Asthma Control (Primary Estimand)		ETP, SAC
2.13.	mITT_LoC	EFF_T05	Summary and Analysis of Time to Loss of Asthma Control (Secondary Estimand)		ETP, SAC
Secondary Endpoints: Hospitalisation and Emergency Room Visits					
2.14.	mITT	EFF_T06	Summary and Rate of Asthma-Related On-treatment Hospitalisations and Emergency Room Visits (Primary Estimand)		ETP, SAC
Secondary Endpoint: ACQ-5 and SGRQ					
2.15.	mITT	EFF_T07	Summary of Raw and Change from Baseline in ACQ-5 Total Score (Primary Estimand)		ETP, SAC
2.16.	mITT	EFF_T07	Summary of ACQ-5 Responders (Primary Estimand)		ETP, SAC
2.17.	mITT	EFF_T07	Summary of Raw and Change from Baseline in SGRQ Total Score (Primary Estimand)		ETP, SAC

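### The exposure rule for participants who die has no cap at last dose + 28 days, so a death in follow-up adds days that the plan itself treats as off treatment

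*SAP*

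**What the plan says.** Section numbers are those of the amended plan.

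- **Basis of exposure (12.6.2, Extent of Exposure).** The plan has "each dose viewed as providing therapeutic coverage for 4 weeks (28 days"). Exposure in days is last dose date minus first dose date plus 29.
- **Death exception (same section).** "The only exception to this will be when a participant dies in which case" the duration becomes death date minus first dose date plus 1. No condition is placed on when the death occurs.
- **Dosing (2.4).** Four infusions are given "intravenously (Week 0, 4, 8 and 12"), which the schedule in 12.2.1 places on study days 1, 29, 57 and 85.
- **On-treatment window (12.4.1 and 12.4.2).** For all data except efficacy, and for treatment-emergent adverse events, the window closes at treatment stop date + 28 days. For efficacy data it closes at the same point, or at discontinuation for participants who stop early. Later dates are post-treatment. A 12-week follow-up comes after treatment.
- **Use of exposure.** Section 12.6.4 gives "Rate = number of events * 1000 / total treatment exposure in years". Table 2.1, "Summary of Exposure to Study Treatment", is due at both the end-of-treatment and the final deliveries.

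**The concern.** The general formula and the exception have different end points. The general formula stops the clock when the last infusion's coverage ends. A death exception makes sense only if it stops the clock sooner, because the participant died before that coverage ran out. As written, it replaces the general formula for every death. For a death after coverage has ended, it moves the end point later.

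Two things are at stake. The first is the individual value in Table 2.1: a participant reported with 113 days at the end-of-treatment delivery could appear with up to 197 days at the final one, with no further infusion given. The second is consistency between numerator and denominator. Days after last dose + 28 would enter total exposure, while events on those days are classed as post-treatment and stay out of an on-treatment count.

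**Working it through.** **Inputs**
- Infusion days 1, 29, 57, 85 (2.4 and 12.2.1).
- Coverage of 28 days per dose, and both exposure formulas (12.6.2).
- Follow-up of 12 weeks = 84 days (12.4.1). Week 28 is Day 28 × 7 + 1 = 197.
- 70 participants per arm, from the sample size statement in 2.6, used here only to size the effect.

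**1. Reproduce the plan's own figure.** On schedule, the general formula gives 85 - 1 + 29 = 113 days. This agrees with 7.2.4.1, where completers "will be censored at 113 days (16 weeks + 1 day"). The +29 is therefore last dose + 28 with inclusive day counting, and the general formula is sound.

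**2. Apply the death exception, then the same rule capped at last dose + 28.** Capped value = min(death day, last dose day + 28) - 1 + 1.

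| Infusion days | Death day | As written | Capped | Excess |
|---|---|---|---|---|
| 1, 29, 57, 85 | 100 | 100 | 100 | 0 |
| 1, 29, 57, 85 | 113 | 113 | 113 | 0 |
| 1, 29, 57, 85 | 141 | 141 | 113 | 28 |
| 1, 29, 57, 85 | 169 | 169 | 113 | 56 |
| 1, 29, 57, 85 | 197 | 197 | 113 | 84 |
| 1 | 20 | 20 | 20 | 0 |
| 1 | 60 | 60 | 29 | 31 |
| 1 | 95 | 95 | 29 | 66 |

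Up to last dose + 28 the exception does what it should: a death on Day 100 gives 100 days instead of 113. Beyond that point every extra day alive is credited as coverage, although no infusion supplies it.

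**3. Effect on an arm's rate.** The rate is multiplied by (total exposure) / (total exposure + excess).
- Mean exposure 113 days: 70 × 113 = 7,910. One Week 28 death: 7,910 / 7,994 = 0.989, a fall of 1.1%. Two: 7,910 / 8,078 = 0.979, a fall of 2.1%.
- Mean exposure 80 days (assumed, to allow for early withdrawals): 70 × 80 = 5,600. One: 5,600 / 5,684 = 0.985, a fall of 1.5%. Two: 5,600 / 5,768 = 0.971, a fall of 2.9%.
- No death later than 28 days after the last infusion: no change.

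**The case against.** The best defence is that this hardly matters. It needs a death more than 28 days after the last infusion, the plan gives no expected death rate, and one such death moves an arm's rate by about 1%. That stands, and it fixes the point as minor. It does not make the value in Table 2.1 right for the participant concerned.

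A second defence is that no safety table title in 12.10.7 mentions a rate or an adjustment for exposure. That also stands. The one table title in Appendix 10 that announces a rate is Table 2.14, on hospitalisations and emergency room visits, for which 7.2.1 names study treatment exposure in the summary measure. The table shells are not in the document, so use of this denominator elsewhere can be neither shown nor excluded. A reader might infer that the rate of fatal events itself is diluted. A fatal event with onset after last dose + 28 is post-treatment and is not in the on-treatment numerator at all; only the rates of other on-treatment events could move.

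A reader might also go further and object that the general formula counts a skipped infusion as covered: infusions on Days 1, 29 and 85 give 113 days, although three 28-day windows cover only 84. The documents do not support calling this an error that lowers rates. For adverse events the on-treatment window in 12.4.2 runs without a break from first dose to last dose + 28, so events in the gap are counted and numerator and denominator span the same days. Elapsed span or summed coverage is a choice of convention, and the plan states its formula. Removing gap days while leaving the event window alone would create a mismatch of its own, with events left without person-time behind them.

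**Conclusion.** The death exception contradicts its own 28-day basis and the on-treatment window in 12.4 whenever death falls more than 28 days after the last infusion. The excess for one participant reaches 84 days in the worked case of death at Week 28 after four infusions (197 against 113). After one infusion and death on Day 95 it is 66 days (95 against 29). The arm-level effect is small: on-treatment rates using this denominator fall by about 1.1% per Week 28 death, on the assumption of 70 participants per arm averaging 113 days, or 1.5% if the average is 80 days. It is zero without such a death. The finding does not extend to missed infusions, or to a general claim that the trial's safety rates are understated.

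**What to change.** In 12.6.2, replace the formula in the death exception with:

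exposure in days = min(death date, last dose date + 28) - first dose date + 1.

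For a survivor the general formula is unchanged, and for a death within 28 days of the last infusion the result is the same as now. Only later deaths are affected; they get the value that a survivor with the same infusions would have. The cost is one line in the derivation and its program. Leave the first-to-last span as it is, since it matches the adverse event window.

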**12.6.3. Efficacy**

Loss of Asthma Control
Multiple Loss of Asthma Control

 
If a participant reaches loss of control for multiple reasons then all reasons will be reported. For any time to loss of asthma control analysis, the time of the earliest component of loss of control will be used.
 

Date of Loss of Asthma Control
Date of loss of control will be taken from the loss of control log page.

Diary Data

The vendor data captures the date on which the subject completes the diary (actual date of collection) rather than the date to which the questions relate. For example, in the morning diary subjects are asked ‘Did you wake up due to asthma symptoms’ and ‘when you woke up due to your asthma symptoms did you use any rescue bronchodilator?’ In the evening diaries subjects answer a question on daytime asthma symptoms and record the number of puffs of rescue medication used during the day. This means that the morning diary date in the raw data refers to the events during the previous night and that the evening diary relates to the events during the day time.
 
In order to ensure that correct observations are assigned to each four-week time period, measurements recorded in the morning diary will have 1 day removed in the analysis dataset to ensure that the date reflects the time period that the information related to. This adjustment is not required for evening diary as these are collected in the evening of the day to which they relate. Questions which this affects are those where the timepoint reference is MORNING:
 
 
Was evening dose taken?
 
Did you wake up due to asthma symptoms?
 
When you woke up due to your asthma symptoms did you use any rescue bronchodilator?
 
Number of puffs – night time
 
 
PEF assessments will not have the adjustment made as these reflect the PEF as assessed (so the PEF recorded in the morning diary is the PEF at that time).

## 12.6.4. Safety

Adverse Events
Adverse Events of Special Interest (AESI)

Systemic Allergic/Hypersensitivity and Non-allergic Reactions:
 
 
• Hypersensitivity (SMQ) [narrow]
 
• Anaphylactic reaction (SMQ) [narrow]
 
• Angioedema (SMQ) [narrow]
 
 
Alterations in immune response (infections)
 
All infections and serious infections reported under the MedDRA system organ class of 'Infections and Infestations'. Specific events of interest are opportunistic infections with preferred terms matching identified/pre-determined terms based on a published list of pathogens and/or presentations of specific pathogens to be considered as opportunistic infections in the setting of biologic therapy [Winthrop, 2015].
 
Alterations in immune response (malignancies):
 
All neoplasms reported under the MedDRA system organ class of 'Neoplasms, benign, malignant and unspecified (including cysts and polyps)'. Specific events of interest are malignancies which will be identified through matching of collected preferred terms with those from the following:
 
Sub-SMQs under the Malignancies SMQ:
 
 
• Malignant tumours sub-SMQ (narrow terms)
 
• Tumours of unspecified malignancy sub-SMQ (narrow terms)
 
 
Alterations in cardiovascular safety:
 
Cardiac disorders and serious cardiac disorders reported under the MedDRA system organ class of 'Cardiac Disorders'. Serious cardiac, vascular and thromboembolic (CVT) events, identified as all serious events classified under the MedDRA system organ classes of 'Cardiac Disorders' and of 'Vascular Disorders', and thromboembolic events identified through matching of collected preferred terms with those from the following:
 
Sub-SMQs under the Embolic and thrombotic events SMQ:
 
 
• Embolic and thrombotic events, arterial sub-SMQ (narrow terms)
 
• Embolic and thrombotic events, venous sub-SMQ (narrow terms)
 
• Embolic and thrombotic events, vessel type unspecified and mixed arterial and venous sub-SMQ (narrow terms)
 
 
Sub-SMQs under the Ischaemic Heart Disease SMQ
 
 
• Myocardial infarction sub-SMQ (narrow terms)
 
• Other Ischaemic heart disease sub-SMQ (narrow terms)
 
 
Sub-SMQs under the Central Nervous System Vascular Disorders SMQ
 
 
• Ischaemic central nervous system vascular conditions sub-SMQ (narrow terms)
 
• Central nervous system vascular disorders, not specified as haemorrhagic or ischaemic sub-SMQ (narrow terms)
 
• Serious ischemic adverse events, a subset of the serious CVT events identified through matching of collected preferred terms with those from the following:
 
 
Local Injection Site Reactions
 
Local injection site reactions are identifying through preferred terms which had been selected by medical review of the MedDRA dictionary and are provided in a separate spreadsheet.



Rate of Events per 1000 Treatment Years
 
Rate of events per 1000 treatment years will be calculated using:
 
Rate = number of events * 1000 / total treatment exposure in years where subjects can contribute more than one event.
 
This is equivalent to: Rate = number of events * 1000 / (number of subjects in treatment group * mean treatment exposure in years).

--

Maximum/Minimum Definitions for Vital Signs Data
 
Maximum and Minimum: Maximum and Minimum post-randomisation value over all time-points (including scheduled and unscheduled assessments) will be presented.

---

FEV1

Absolute Reversibility
 
Absolute reversibility (mL) = (post-bronchodilator FEV1 – pre-bronchodilator FEV1)

Percent Reversibility
 
Definition of Percentage Reversibility as a percentage of predicted FEV1 = ((post-bronchodilator FEV1– pre-bronchodilator FEV1) / predicted FEV1) x 100%
 
Definition of Percentage Reversibility as a percentage of pre-bronchodilator FEV1 = ((post-bronchodilator FEV1– pre-bronchodilator FEV1) / pre-bronchodilator FEV1) x 100%

## 12.7. Appendix 7: Reporting Standards for Missing Data

### 12.7.1. Premature Withdrawals

Element	Reporting Detail
General	
 
• Subject study completion (i.e. as specified in the protocol) was defined as either completing the 16 week treatment period and three month safety follow up, or withdrawing from the treatment period early due to loss of asthma control and completing the three month safety follow up period.
 
• Withdrawn participants were not replaced in the study, unless the participants were withdrawn due to sites failing to comply with GCP.
 
• All available data from participants who were withdrawn from the study will be listed and all available planned data will be included in summary tables and figures, unless otherwise specified.
 
• Withdrawal visits will be slotted as per Appendix 3: Assessment Windows or will be summarised as withdrawal visits.
 

### 12.7.2. Handling of Missing Data

Element	Reporting Detail
General	
 
• Missing data occurs when any requested data is not provided, leading to blank fields on the collection instrument: 
 
○ These data will be indicated by the use of a “blank” in subject listing displays. Unless all data for a specific visit are missing in which case the data is excluded from the table.
 
○ Answers such as “Not applicable” and “Not evaluable” are not considered to be missing data and should be displayed as such.
 
 
 

Analysis	
 
• All missing data will be handled according to estimand of interest as described within the main body of the RAP.
 

ACQ	
 
• If one of the five items in the ACQ is missing then the response from the four remaining items will be interpolated (pro-rata) to gain the overall response for the participant.
 
• If more than one item is missing then the ACQ will be considered missing.
 

SGRQ	
The SGRQ questionnaire has three components; symptoms, activity and impact.
 
Symptoms
 
 
• The Symptoms component will tolerate a maximum of 2 missed items. The weight for the missed item is subtracted from the total possible weight for the Symptoms component (662.5) and from the Total weight (3989.4)
 
 
Activity
 
 
• The Activity component will tolerate a maximum of 4 missed items. The weight for the missed item is subtracted from the total possible weight for the Activity component (1209.1) and from the Total weight (3989.4)
 
 
Impacts
 
 
• The Impacts component will tolerate a maximum of 6 missed items. The weight for the missed item is subtracted from the total possible weight for the Impacts component (2117.8) and from the Total weight (3989.4)
 
 
If any component has more missing items then mentioned above then the SGRQ will be considered missing.

